### **5.7.2.2 Baclofen dose in opiate dependence**

Our previously conducted pharmacokinetic-pharmacodynamic (PK/PD) study to investigate the sensitivity of the GABA-B system demonstrated that alcohol dependent participants were less sensitive to the subjective and objective effects of baclofen than healthy controls (Durant et al 2018), and evidence from elsewhere suggests the same might be true for opiate dependence (Volpi et al., 1992).

Details of all previous studies (to our knowledge) investigating baclofen in opiate dependence are provided in Table 1 and section 2.4. Doses of baclofen ranged from 40 to 80mg/day. No safety issues were reported, and baclofen was described as well tolerated with few adverse events.

More specifically, Krystal et al (1992) reported that 80 mg/day of baclofen was tolerated without evidence of side effects in patients whose methadone was abruptly stopped. In the Iranian studies of opiate detox, data was not presented regarding side-effects in one (Akhondzadeh et al., 2000). The other reported no overall difference in side-effect profile with baclofen compared with clonidine however, headache, nausea and vomiting were seen more with baclofen and dry mouth and orthostatic hypotension more with clonidine (Ahmadi-Abhari et al., 2001). No difference was reported in side-effects or adverse events between baclofen and placebo during a trial for relapse prevention in opiate dependence (Assadi et al., 2003).

### **5.7.3 Pharmacy and packaging**

Drugs will be stored at Hammersmith hospital (HH) pharmacy and dispensed according to the prescription, which will be completed by the study physician. Dispensing and management of drug accountability will be managed and conducted by HH Pharmacy according to their SOPs. Prescriptions & Drug accountability logs will be maintained by the research team.

### **5.7.3.1 Baclofen**

Baclofen (generic) will be supplied by Imperial College Healthcare NHS Trust pharmacy (Hammersmith Hospital). These are white, round, scored tablets. Labelling will be as per Annex 13 regulations and dispensed under Regulation 37 of the 2004 UK Clinical Trial Regulations within the hospital, according to the exemption contained therein.

### **5.7.3.2 Placebo**

Placebo tablets will be vitamin D3, (colecalciferol; scored, white round tablets) that are a near identical match to baclofen, supplied by Imperial College Healthcare NHS Trust pharmacy (Hammersmith Hospital). Labelling will be as per Annex 13 regulations and dispensed under Regulation 37 of the 2004 UK Clinical Trial Regulations within the hospital, according to the exemption contained therein.

### **5.7.4 Emergency Unblinding Procedure**

This is single-blind- study clinicians and researchers will be aware of the drug allocation that was recommended by the adaptive trial algorithm and this allocation will be stored within the OpenClinica Database and accessible to the research team.

## **5.8 Study Durations**

### **5.8.1 Protocol in event of experimental day failure**

In the event that a participant does not attend as planned, or tests positive for alcohol or drugs of abuse, or is ineligible for the study day (e.g. positive covid test, illness) prior to baclofen administration, the experimental visit will be re-scheduled. The participant would retain their baclofen or placebo randomisation, and their baclofen dose allocation. However, depending on the length of time between the cancelled and re-scheduled visit, and the potential for updates to the adaptive model in the intervening time, the baclofen dose level may be re-allocated, according to the discretion of the Dose Setting Committee.

In the event that a participant has been administered medication during an experimental study visit, and there is subsequently a problem (e.g. fire alarm, non-recoverable equipment malfunction), that results in significant data loss such that the participant does not meet criteria for an evaluable participant, with the continued consent of the patient the study day (including drug administration) will be repeated at another scheduled session (in at least 5 days' time if participant was randomised to baclofen).

In the event that a participant does not re-schedule and is considered 'lost', that participant can be replaced if required (i.e. to make total of 48 on baclofen if safety has not yet been established). The replacement participant should receive the same treatment (placebo or baclofen) of the participant that is being replaced. However, in this case, the baclofen dose level may be re-allocated, as informed by the current model based on the replacement person's own methadone dose, and at the discretion of the Dose Setting Committee.

### **5.8.2 Withdrawal of Participants from the Study**

Participants can initiate withdrawal from the study. Each patient that will be recruited has the right to withdraw from the study for any reason. All data and samples collected to date will be retained. Should a participant decide to withdraw from the trial, all efforts

will be made to report the reason for withdrawal as thoroughly as possible and they will be encouraged to continue to provide outcome data.

#### **5.8.3 Duration of the study period**

The duration of the study period will be approximately 2-3 weeks for participants to complete consent, screening, experimental study visit and follow-up. In the event of a longer delay between screening and experimental visit, certain screening activities may be repeated at the discretion of the clinical team.

#### **5.8.4 Flexible visits**

We wish to minimise the drop-out rates and make participation as easy and flexible for participants as possible (particularly opiate dependent). Therefore participants may decide to undertake certain screening assessments over several visits, e.g. they may wish to participate by phone, online video or via an in-person visit in their local addiction service rather than at the ICRF. Subject to the relevant HRA approvals being in place, flexible visits for this purpose will be permitted.

#### **5.8.5 Duration of the follow-up period**

The duration of the follow up period will be 1 day for all participants who will receive a phone call the day after the experimental study visit.

#### **5.8.6 Loss to follow-up**

It is anticipated that more subjects will complete initial screening assessment than the experimental visit. Unless participants actively withdraw participation, data will be retained and analysed, as appropriate.

#### **5.8.7 Definition of completion of the study for an individual participant**

The end of the study will be defined as the last telephone contact visit which is 1 day after their study visit for opiate dependent participants. This represents the end of data collection as defined in ethics and regulatory terms, after which, adverse events will not be recorded.

#### **5.8.8 Definition of the end of the study**

The completion of the study for regulatory purposes will be defined as the last telephone follow-up appointment for the last participant.

### **6 PARTICIPANT RECRUITMENT**

#### **6.1 Population**

Opiate dependent participants enrolled in this study will be engaged in treatment for their opiate dependence from a specialist community addiction service and receiving stable doses of opiate substitution therapy with methadone. Therefore the participants will be regularly attending an addiction service, receiving psychosocial support. Therefore participants will not be chaotic with regard to their drug/alcohol use, unreliable in their attendance at appointments or have substantial physical or mental health needs.

In particular, the research team will endeavour to recruit participants from across the methadone-maintenance dose range, including both males and females, to maintain a

balanced design and to capture data that allows a representative assessment of safety across the clinical population.

## **6.2 Number of Participants**

The sample size is not fixed. Up to a total of 64 patients are planned to be enrolled in the study with up to 48 patients on the experimental doses and up to 16 on placebo, as recommended by the trial algorithm in consultation with clinicians and the study team.

The drop-out rate from the study is estimated to be approximately 20% following screening. We therefore anticipate screening up to 100 methadone-maintained opioid dependent participants for entry into the study, with ~75% eligibility rate at screening, and a further ~20% drop out prior to, or at the experimental session.

### ***6.2.1 Definition of successful completion***

Successful completion will be defined as those meeting criteria for an 'evaluable patient' as defined in section 3.4.7. In the event of incomplete data, we will make a decision as to whether an individual's data will be included in the primary and secondary analyses on a case-by case basis.

For primary analysis, we will endeavour to include all those who received baclofen, if data allows a determination of whether or not a DLT was deemed to have occurred, according to clinical judgement.

For secondary outcomes, analyses will include those that have at least one measurement following drug administration.

## **6.3 Recruitment Strategies**

Opiate dependent individuals will primarily be recruited from NHS substance misuse services and/or related voluntary sector services based in London and surrounding areas, by directed advertisement at those services, via referral, or via an investigator-led approach at NHS trusts, voluntary sector or partner organisations via Participant Identification Centres (PIC) or equivalent, subsequent to relevant approvals. Increasing visibility of the study and additional recruitment channels may also involve widespread advertisement in social media, dedicated study facebook pages or social media presence, and advertising on relevant websites related to addiction.

All advertising webpages will contain a link to a dedicated FORWARDS study website and/or email address which will provide a basic resource for further information, and study contacts such that the study team can contact participants as appropriate.

## **6.4 Eligibility Criteria**

### ***6.4.1 Inclusion Criteria***

1. Male or female
2. Aged over 21
3. Willing and able to comply with protocol

4. Able to read, comprehend and record information written in English
5. Capable of giving written informed consent, which includes compliance with the requirements and restrictions listed in the consent form.
6. Healthy as determined by a responsible physician, based on a medical evaluation which includes medical history, a physical examination, laboratory tests (if required), and a psychiatric evaluation. A volunteer with clinical parameters outside the reference range for the population being studied may be included, only if the investigators concur that the finding is unlikely to jeopardize either subject safety or study integrity.
7. DSM-5 diagnosis of current severe opioid use disorder
8. Treated with methadone substitution therapy and able to maintain the same stable dose for screening and experimental visit.
9. Ability to receive an acute dose of up to 90mg baclofen or up to 4800IU vitamin D (placebo).

#### **6.4.2 Exclusion Criteria**

A subject will not be eligible for inclusion in this study if any of the following criteria apply:

1. Intoxication on any of the visits, as assessed by difficulty in walking, the slurring of speech, difficulty concentrating or drowsiness. This exclusion criteria would exclude a subject from that study day only and not the whole study, at the discretion of the research team.
2. Positive urine drug screens or breath alcohol at screening or experimental testing visits. A minimum list of drugs that will be screened for include amphetamines, cocaine, opiates, methadone, cannabinoids and benzodiazepines. Positive results for methadone will be allowed for those opiate dependent participants still undergoing OST. Positive results for cannabinoids will be allowed given the long half-life of cannabinoid metabolites. This exclusion criteria would exclude a subject from that study day only and not the whole study, at the discretion of the research team.
3. Current DSM-5 substance dependence disorder for any other substance except for opiates and nicotine. Lifetime history of dependence on other substances will be allowed given very high incidence of co-dependence.
4. Regular on-top use of heroin or other opiates or other illicit substances in combination with OST, which in the opinion of the investigators will interfere with subject safety or study integrity.
5. Any participant taking over 120mg/day of prescribed methadone.
6. Current severe DSM-5 mental health disorder (excluding opiate dependence). Current moderate or mild DSM-5 depressive, anxiety, sleep or personality disorders will be allowed given the high levels of comorbidity, provided in the opinion of the investigators, the participant is able to complete study procedures satisfactorily.

7. Current or past history of enduring severe mental illness e.g. psychotic disorder (excluding drug induced), schizophrenia, bipolar affective disorder).
8. Active suicidality.
9. Use of regular prescription medications which in the opinion of the investigators will interfere with subject safety or study integrity. Regular use of psychotropic medication will be permitted e.g. antidepressants, provided the participant is compliant with administration and the investigators concur that they will not interfere with subject safety or study integrity.
10. Participants are taking any medication that is contraindicated with baclofen or placebo (vitamin D3), or are hypersensitive to them or any of their excipients.
11. Participants that are taking any medication that in the opinion of the investigators may impact on the outcome measures during the experimental session.
12. Use of intermittent psychotropic medication which in the opinion of the investigators will interfere with subject safety or study integrity.
13. End stage or acute renal failure.
14. Severe chronic obstructive pulmonary disease (COPD) or Type 2 respiratory failure.
15. Pulse rate <40 or >100 BPM OR systolic blood pressure >160 and <100 and a diastolic blood pressure >95 and <60 in the semi-supine position.
16. Oxygen saturation <92% at rest
17. A screening ECG with a QTcB or QTcF > 500 msec or an ECG that is not suitable for QT measurements (e.g. poorly defined termination of the T-wave) and/or with another ECG abnormality which in the opinion of the study physician is clinically significant and represents a safety risk. Note that if the initial QTc value is prolonged, the ECG should be repeated two more times (with 5 minutes between ECG readings) and the average of the 3 QTc values used to determine eligibility.
18. Clinically significant head injury (e.g., requiring medical or surgical intervention) that in the opinion of the investigators, contraindicates their participation .
19. Active hepatitis or HIV.
20. Active peptic ulceration.
21. Significant current or past medical history that, in the opinion of the investigators, contraindicates their participation.
22. The subject has participated in a clinical trial and has received an investigational product within 30 days, 5 half-lives or twice the duration of the biological effect of the investigational product (whichever is longer) prior to the first experimental visit.

23. Pregnancy or breast-feeding
24. Unwillingness or inability to follow the procedures outlined in the protocol.

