Cases of sleep disordered breathing have been reported amongst those taking chronic baclofen e.g. central sleep apnoea in four individuals receiving chronic baclofen for alcohol withdrawal (NB n=3 were taking >150mg daily, (Olivier et al., 2016)), which was subsequently managed by adaptive servo-ventilation or baclofen cessation. In contrast, in a study of susceptible snorers baclofen (25mg) did not alter sleep disordered breathing (Finnimore et al., 1995). Chronic opioid use, including methadone, is also associated with central sleep apnoeas (Correa et al., 2015).

Due to the inherent risks of combining CNS depressant drugs such as baclofen and methadone, and the vulnerability of this patient group, we will seek to understand whether any respiratory, sedative and cardiovascular effects occur following baclofen administration in combination with methadone in a single ascending dose study, incorporating pharmacokinetic-pharmacodynamic measures.

Monitoring of both cardiovascular and respiratory function will occur, and both will be assessed for significant clinical impairment at screening and forms part of the exclusion criteria.

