### **5.2.4 Vital statistics and Vital signs**

Height, weight and body mass index will be measured. Vital signs will comprise systolic and diastolic blood pressure, pulse rate, body temperature and blood oxygenation.

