## **8 STATISTICS AND DATA ANALYSIS PLAN**

### **8.1 General statistical principles**

No formal statistical testing will be conducted for this early phase study and no power calculation has been performed; all statistical analyses for primary and secondary outcomes are to be viewed as exploratory.

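### The blood-pressure part of exclusion 15 joins its limits with *and*, so no measurement can meet it, and the text does not say how systolic and diastolic combine

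*Combined protocol and SAP*

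**What the plan says.** Section 6.4.2 opens with "A subject will not be eligible for inclusion in this study if any of the following criteria apply", so meeting any one numbered item is enough to exclude. Item 15 has a pulse part and a blood-pressure part. It begins "Pulse rate <40 or >100 BPM OR systolic blood pressure >160 and <100", and the blood-pressure part in full is "systolic blood pressure >160 and <100 and a diastolic blood pressure >95 and <60 in the semi-supine position". The pulse limits are joined by *or*, and a capital *OR* separates pulse from blood pressure. Every join after that is *and*.

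The measurements needed to apply the item are taken. Section 5.2.4 states: "Vital signs will comprise systolic and diastolic blood pressure, pulse rate, body temperature and blood oxygenation". No other section repeats the blood-pressure limits or explains how to read them.

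Two other entries allow judgement. Inclusion 6 (section 6.4.1) says: "A volunteer with clinical parameters outside the reference range for the population being studied may be included, only if the investigators concur" that safety and study integrity are unlikely to suffer. Exclusion 21 covers "Significant current or past medical history that, in the opinion of the investigators, contraindicates their participation". In more general terms, section 2.6 says of cardiovascular and respiratory function that "both will be assessed for significant clinical impairment at screening and forms part of the exclusion criteria".

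**The concern.** An eligibility limit should give the same answer whoever applies it. This one has two faults.

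First, each pair of limits asks one number to be in two places at once, so the condition is never true.

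Second, the obvious mental correction, changing *and* to *or* inside each pair, leaves open the *and* that joins systolic to diastolic. One person may take it as a list of excluded values, so that either pressure out of range excludes. Another may take it as a joint requirement, so that both must be out of range.

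What is at stake is whether a volunteer with one pressure outside the stated limits is excluded by rule or left to individual judgement. If the item is programmed as an edit check in the trial database, someone has to choose a reading, and the literal one would never fire.

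**Working it through.** The plan has no figure to reproduce here. Section 8.1 states that "No formal statistical testing will be conducted for this early phase study and no power calculation has been performed", and the question is one of logic. The inputs are the four limits in item 15 (systolic 160 and 100, diastolic 95 and 60). All are strict inequalities, so 100 to 160 and 60 to 95 inclusive count as in range.

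Write S for systolic and D for diastolic. Three readings of the blood-pressure part:

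- As written: (S > 160 *and* S < 100) *and* (D > 95 *and* D < 60)
- Repair A, *or* throughout: S > 160 *or* S < 100 *or* D > 95 *or* D < 60
- Repair B, *or* within each pressure and *and* between them: (S > 160 *or* S < 100) *and* (D > 95 *or* D < 60)

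**Step 1: as written.** S > 160 and S < 100 have no value in common; nor do D > 95 and D < 60. Both brackets are empty, so the whole condition is empty.

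**Step 2: example measurements.**

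| S/D (mmHg) | As written | Repair A | Repair B |
|---|---|---|---|
| 120/80 | not caught | not caught | not caught |
| 95/70 | not caught | excluded | not caught |
| 170/80 | not caught | excluded | not caught |
| 150/100 | not caught | excluded | not caught |
| 110/55 | not caught | excluded | not caught |
| 95/55 | not caught | excluded | excluded |
| 165/100 | not caught | excluded | excluded |

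**Step 3: a full grid as a check.** Take every whole-number pair with S from 70 to 220, D from 30 to 140 and D below S.

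- Total: 151 × 111 = 16,761 pairs, less the 71 × 72 / 2 = 2,556 with D at or above S, leaves 14,205.
- As written: 0 excluded.
- Repair A: all pairs except those with both pressures in range. There are 61 × 36 = 2,196 of those, so 14,205 − 2,196 = 12,009 excluded.
- Repair B: S from 161 to 220 with D out of range gives 60 × 75 = 4,500. S from 70 to 99 with D from 30 to 59 gives 30 × 30 = 900. A further 6 pairs have S from 97 to 99 and D from 96 up to just below S. The sum is 5,406.
- Caught by A but not B: 12,009 − 5,406 = 6,603.

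Every pair caught by B is also caught by A. The grid shows only that the repairs differ and in which direction. It weights all pairs equally, so its counts are not shares of participants.

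**The case against.** The strongest reply is that this is an editorial slip that no clinician would act on. The self-contradictory version would never be applied. Treating each *and* as listing a further excluded range handles all three joins alike and gives *or* throughout. Repair B, by contrast, needs the same word to mean *or* twice and *and* once within one clause. Most screening takes place at a single facility (section 5.2.1), and eligibility is checked again there on the dosing day (section 5.4.1), so one team could apply one reading. The database requirements mentioned in section 9.3.3 may already fix the rule.

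Much of this stands. *Or* throughout is the more natural repair, and literal use is unlikely. But the same sentence uses *or* for pulse and a capital *OR* before blood pressure, then changes to *and*, so a joint requirement is not a perverse reading. Section 5.2.1 also allows screening at a partner-trust clinic. The database requirements are not in these documents, so they cannot be relied on either way.

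A reader might also infer four stronger claims, none of which the documents support:

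- *Item 15 is void.* It is not; the pulse part can be met.
- *A volunteer at 95/70 or 170/80 is admitted.* Not caught by item 15 is as far as the text goes. Inclusion 6 requires a physician to judge the volunteer healthy, and exclusion 21 still applies.
- *Section 2.6 depends on this item.* That section names neither blood pressure nor item 15, and the ECG exclusion (item 17) also screens cardiovascular function.
- *Participants in dispute carry a different background risk of a DLT.* Systolic pressure is a NEWS2 parameter (section 5.4.6) and NEWS2 enters the DLT definition (section 3.4.2). The documents do not give the NEWS2 scoring bands for systolic pressure, so no difference in risk can be derived.

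**Conclusion.** The point holds as a wording error in an operative safety criterion. Taken literally, the blood-pressure part of exclusion 15 excludes nobody, which follows from the four stated limits without any further assumption. Once repaired, it has at least two meanings that classify a volunteer with a single out-of-range pressure differently, and nothing else in the protocol settles the choice. The discretionary entries soften the practical effect but supply no limit and no rule for combining the pressures.

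The number of participants affected cannot be stated, because it depends on a blood-pressure distribution that the documents do not give. No effect on the dose-toxicity model, the DLT definition or the stopping rules is shown. The item is worth correcting because it is wrong as written and easy to repair.

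**What to change.** Restate item 15 with an explicit connector at every join, using brackets or separate sub-items, so that the blood-pressure part can be met and has a single meaning. State whether one out-of-range pressure is sufficient or both are required. The clinical team should make that choice; this review takes no position on it. No limit value needs to change. If the eCRF has an eligibility check for this item, align it with the new text.

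The cost is one sentence in the protocol and, where it exists, the matching edit check.
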